1. SYNOPSIS

Sponsor's Identification and Address	IPSEN PHARMA, S.A. [name]. [contact] [contact]
Study Title	Post-approval observational prospective study to evaluate the prevalence of the metabolic syndrome in prostate cancer patients both before and after a 12-month treatment with quarterly LHRH analogue formulations (ANAMET Study).
Protocol Code (according to official coding standards)	IPS-TRI-2008-01
Co-ordinating Investigator and his/her Address	PPD Hospital Vall d' Hebron [name]
Type of Centres where the Study is Anticipated to be Carried Out	The study will be carried out at the Urology and/or Radiation Therapy Services of different hospitals throughout the Spanish territory.
Evaluating ECCR	Hospital Vall d'Hebron's ECCR
Primary Objective	The objective of this study is to assess the prevalence of the metabolic syndrome in accordance with the NCEP ATP III Panel definition in patients with prostate cancer both before and after 12-month treatment with quarterly LHRH analogue formulations.

Design	ANAMET is a post-approval observational, prospective, multicentre and open study to assess the prevalence of the metabolic syndrome in patients with prostate cancer both before and after 12-month treatment with quarterly LHRH analogue formulations.
Disease or Disorder Studied	Male prostate cancer patients.
Data of the Studied Drugs	
The patients included in the study will receive treatment with LHRH quarterly analogues.
 
The LHRH analogues commercialised in our country are:
 
 - buserelin (9.45 mg quarterly implant; SC injection), - goserelin (10.8 mg quarterly implant; SC injection), - leuprorelin (22.5 mg quarterly injection; SC injection), - leuprorelin (22.5 mg quarterly injection; IM injection), and - triptorelin (11.25 mg quarterly injection; IM injection).
Study Population and Total Number of Subjects	
Patients diagnosed with prostate cancer and scheduled to receive a long-term (12 months) treatment with LHRH quarterly analogues.
 
Inclusion Criteria
 
 - Patients should give their written informed consent (personally signed and dated) before starting with any study-related procedures. - Patients should be 18 years old or over. - Patients should have a histology-confirmed prostate cancer diagnosis, and be eligible for either continuous androgen deprivation therapy or treatment with LHRH analogues in accordance with the specifications of the relevant data sheets for a period of at least 12 months.

	
- Patients should have an estimated survival expectancy of at least 12 months in the investigator's opinion.
 
Exclusion Criteria Any patient currently on or having previously received androgen deprivation therapy.

Schedule
	
Inclusion of the first patient is foreseen to take place on the first quarter of 2009, and treatment completion by the last patient is foreseen to occur on the first quarter of 2011.

Financial Sources
	
As the sponsor of the study, IPSEN PHARMA, S.A will meet all expenses originated by same.

3. GENERAL INFORMATION

Code

IPS-TRI-2008-01

Title

Post-approval observational prospective study to evaluate the prevalence of the metabolic syndrome in prostate cancer patients both before and after a 12-month treatment with quarterly LHRH analogue formulations (ANAMET Study).

Data on the Sponsor/the Monitor

IPSEN PHARMA, S.A.

[name].

[contact] [contact]

The staff from the IPSEN PHARMA, S.A.'s Medical Department will be responsible for monitoring the observational study.

Centres and Autonomic Communities where the Study is Anticipated to be Carried Out

The study shall be carried out with the participation of urologists and radiation therapists from different hospitals throughout the Spanish territory.

Annex 7 to this protocol shows the interim list of Autonomic Communities, centres and principal investigators of this study.

Foreseen Length

The first patient is foreseen to be included in the study on the first quarter of 2009, and the last one on the first quarter of 2010. The last patient is foreseen to complete the study on the first quarter of 2011.

4. STUDY RATIONALE: CRITICAL REVIEW OF LITERATURE

4.1 Review of the Disease

4.1.1. Prostate Cancer

Prostate cancer is currently considered one of the most frequent cancers in men (first in incidence and third in mortality) (1). Most of the cases are localised cancers at the time of diagnosis, and so apt to be adequately treated with surgery and/or radiation therapy (brachytherapy, external-beam radiation therapy, etc.).

More than one third of them appear in locally advanced stages, notwithstanding the screening campaigns. These patients, generally with stages T3 (capsule involvement, vesicle involvement), T4 (nearby organ involvement), N+ (nodal involvement) or M+ (distant, basically bone, involvement), will be candidates to treatment with either complete or partial hypothalamic-pituitary axis blockade.

Indications for hormone blockade are the following: a) as the first option in systemic disease; b) as adjuvant following curative pelvic-prostatic radiation therapy for 2-3 consecutive years; c) as neoadjuvant prior to a 6-month radiation therapy treatment.

Two/three-year treatment concomitant to radiation therapy yields 5- and 8-year disease-free survival rates of around 78% in high-risk locally-advanced disease (Gleason histological grade equal to or higher than 8, PSA > 20 ngr, T equal to or higher than 3, N +, M0).

Treatment with LHRH agonists is not devoid of adverse reactions. In some cases there is a transient exacerbation of the clinical symptoms (basically bone pain) when treatment starts. Some cases of worsening of a preexisting haematuria, or urinary obstruction and/or a sensation of weakening or paresthesia of the lower limbs have been described with the LHRH analogues at treatment initiation. These symptoms are generally transient and they disappear on the first or the second week without requiring treatment discontinuation. In any case, the possibility of an initial symptom exacerbation should be born in mind when treating neurologically affected patients or patients suffering from urinary obstruction.

The following adverse reactions have been described during the treatment: hot flushes, pain at the site of injection, erectile dysfunction and transiently elevated arterial blood pressure that resolves spontaneously.

There are, however, other potential adverse reactions that could be considered significant and that have not as yet been studied in depth, such as the effect of castration (a consequence of the treatment with LHRH analogues) on the patient's metabolic profile.

4.2 Literature Review

Androgens participate decisively of the male body composition. Serum testosterone concentrations are positively correlated to the muscular mass, and negatively to the body fat. In prostate cancer, changes in the body composition are deemed to be the adverse effects of androgen deprivation, although the effects of such deprivation have not been well defined as yet. In a study in which the effects of GnRH agonists on patients with locally advanced prostate cancer, with either positive nodes or recurrent prostate cancer were studied, weight and fat mass gain was appraised. However, weight loss and the disease symptoms before

starting the treatment made it difficult to determine whether the body composition changes were due to hypogonadism or to a treatment-related symptom improvement (2).

To this date, all the studies carried out on androgen deprivation and the development of the metabolic syndrome have been retrospective (4, 5, 6, 7, 8 and 9), or else performed on a reduced number of subjects (11).

5. OBJECTIVES

5.1. Primary Objective

The objective of this study is to assess the prevalence of the metabolic syndrome according to the NCEP ATP III Panel definition in men with prostate cancer both before and after a 12-month treatment with quarterly LHRH analogues formulations.

5.2. Secondary Objectives

Modifications of the parameters below at the baseline visit, at 6 months and at 12 months will be assessed as secondary objectives:

- Physical exploration:
 - i. BMI
 - ii. Blood pressure
 - iii. Weight
 - iv. Abdomen perimeter

- Laboratory tests:
 - i. HbA1c
 - ii. Haemoglobin
 - iii. Triglycerides

- iv. Total, LDL and HDL cholesterol
- v. PSA
- vi. Total testosterone
- vii. Glycaemia
- viii. C-Reactive Protein

6. SOURCE OF INFORMATION AND SCOPE

This study will be conducted according to the usual clinical practice, on patients with prostate cancer who will be submitted to continuous androgen deprivation therapy for at least one year.

7. STUDY DESIGN

Definition of the Study Population: Selection Criteria

This study will include patients diagnosed with prostate cancer who are scheduled to receiving long-term treatment (12 months) with quarterly LHRH analogues.

All patients will be evaluated by means of the following inclusion and exclusion criteria:

• Inclusion Criteria

In order to be eligible for this study, the patients should satisfy the following criteria:

- Give their written informed consent, (personally signed and dated) before starting with any study-related procedures.
- Be 18 years old or over.
- Have a histology-confirmed prostate cancer diagnosis, and be eligible for either continuous androgen deprivation therapy or treatment with LHRH

analogues in accordance with the specifications of the relevant data sheets for a period of at least 12 months.

- Have an estimated survival expectancy of at least 12 months in the investigator's opinion.

• **Exclusion Criteria**

Patients satisfying any one of the following criteria will not be eligible for the study:

- Being administered or having previously been administered with an androgen deprivation therapy.

Observation Period

The observation period for each patient will be 12 months.

Treatment Description and Definition of Exposure

Patients on treatment with quarterly LHRH analogues over 12 months due to prostate cancer, in accordance with the indications described in the products' data sheets.

Also, all patients will receive anti-androgen treatment for one week before and two weeks after receiving the first injection of LHRH analogues.

Concomitant Treatments

All concomitant medications, particularly those treating significant aspects of the metabolic syndrome, such as hypolipemiating, anti-hypertensive, hypoglycaemiating, etc. agents, should be reported. Any dietary or physical activity modification experienced by the patients during the 12-month follow-up should also be reported.

Selection of the Control Group

Not applicable.

Previous Determination of the Sample Size

We assume that the prevalence of the metabolic syndrome (MS) among patients at study initiation will amount to 30%, and that it will increase a further 2% during the study. Increase of over 5% is considered clinically significant.

If we assume that the increased prevalence of the metabolic syndrome will be less than 5%, that 1% of the subjects with baseline MS will not show it at the end of the study, and having established an alpha value of 5%, 500 patients are necessary to have a statistical power of 80%. If we assume 10% of dropouts, 556 subjects are necessary.

8. VARIABLES AND MEASURING INSTRUMENTS. MEASUREMENTS DEFINITION AND DESCRIPTION

8.1. Primary Objective Measurement Variables

The parameters described by the NCEP ATP III Panel for the diagnosis of metabolic syndrome will be applied. Three or more parameters must be above the upper limits for the following variables:

1. Abdominal obesity (abdomen perimeter) > 102 cm
2. Triglycerides ≥ 150 mg/dL
3. HDL-cholesterol < 40 mg/dL
4. Blood pressure $\geq 130/85$ mmHg
5. Fasting glycaemia ≥ 110 mg/dL

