8.3. Sample Size Determination

If we assume:

- 1) metabolic syndrome (MS) prevalence = 30% at study initiation,
- 2) that such prevalence will increase by 2% along the study,
- 3) that 5% of prevalence increase is clinically not significant,
- 4) that $\alpha = 5\%$ (unilateral) and power = 80%, and that we mean to demonstrate that the increase of MS prevalence will be lower than 5% (non-inferiority study)

Using 500 subjects, the upper limit of the unilateral confidence interval (CI) observed of 95% will be expected to be lower than 0.050 with a power of 80% when the expected difference, $p_T - p_S$, D_1 , is 0.020 and the proportion of discordants, $h = p_{10} + p_{01}$, is 0.070, and the proportion yes in both cases, p_{11} , is 0.290. The results are based on 5000 simulations that used the Newcombe-Wilson's score method to produce the confidence interval (Newcombe RG (1988): *Improved confidence intervals for the difference between binomial proportions based on paired data*. *Statistics in Medicine* 17:2635-2650).

Considering a 10% dropout rate, the final sample size is $500/0.9 = 556$ subjects. The recruitment of 556 subjects from some 60 Spanish centres has been devised. Each of the centres will be requested to enlist them following a chronological order based on the date of the first visit carried out at the centre.

Assuming this sample size, the MS prevalence will be estimated with a precision of 0.038 (for a 5% bilateral alpha).

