9.4.4. Evaluation of Efficacy

As stated in section 8.1., the primary variable will be the prevalence of the Metabolic Syndrome according to the ATP III Panel definition, i.e. the presence of three or more risk factors, as shown by the table below:

Table II.6-1. Clinical Identification of the Metabolic Syndrome *

Risk Factor	Level of Definition
Abdominal obesity	Abdominal perimeter [†] > 102 cm
Triglycerides	≥ 150 mg/dl
HDL-cholesterol	< 40 mg/dl
Blood pressure	≥ 130/85 mmHg
Fasting glucose	≥ 110 mg/dl

* The ATP III Panel found no suitable evidence for recommending that the usual insulin-resistance determination (e.g. plasma insulin), the proinflammatory status (e.g. high-sensitivity C-reactive protein) or prothrombotic status (e.g. fibrinogen or PAI-1) be performed for diagnosing the metabolic syndrome.

[†] Some men may have many metabolic risk factors even when their abdominal perimeter is just slightly enlarged, e.g. 94 – 102 cm. The resistance to insulin in those persons may have a strong genetic component. A change of habits may be beneficial to them and also to those men with a far more enlarged abdominal perimeter.

The difference between Metabolic Syndrome at baseline and at study completion will be calculated, and also the 90% confidence interval associated to it in accordance with paired data. Newcombe's method 10, 1998c, will be used with this purpose. If the CI's upper limit were lower than 5%, it may be concluded that a clinically not significantly increased prevalence of SM was found in the study.

The secondary parameters are: BMI, Blood pressure, Weight and Abdominal perimeter.

Regarding secondary parameters, statistics will only be issued including confidence intervals based on the raw data from every evaluation; the analyses will be stratified as per the status of the Metabolic Syndrome.

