9.4.5. Evaluation of Safety

All the safety data will be included in the subjects' data lists. Tabulated analyses and summaries will be based on the general population.

As this is a non-interventional study, only treatment-related Adverse Events (AEs) will be recorded. The AEs will be classified according to the Medical Dictionary for Regulatory Activities (MedDRA), using the term and the organic system class preferred by MedDRA. The AE lists shall be submitted by subject, organic system class and preferred term.

The incidence of all treatment-related emergent AEs (TRAEs) and all SAEs reported will be tabulated. Additionally, tabulated summaries according to maximum severity, relationship with the drug and also AEs/TRAEs associated with early withdrawal of the study medication will be submitted.

TRAE is defined as any AE occurring during the active phase of the study, provided that:

- it had not occurred before receiving the first dose of study drug, or
- it had occurred before receiving the first dose of the study drug but its severity increased in the course of the active phase of the study, or
- it had occurred before receiving the first dose of the study drug, its severity was the same but its relationship to the study drug was established in the course of the active phase of the study.

Treatment-related emergent AEs shall be marked with (*) in the lists of AEs.

Concomitant medication will be coded according to the WHO Drug Dictionary, and summarised including the number and percentage of subjects receiving concomitant medication as <drug class and preferred drug name>.

The statistical summary (mean, median, SD and interval, if applicable) will be displayed by treatment group and also overall regarding heart rate determination and laboratory tests at each assessment, and the changes occurred from baseline will be highlighted. As to the analytical data (including Fasting glucose, HbA1c, Haemoglobin, Triglycerides, Total cholesterol, LDL-cholesterol, HDL-cholesterol, Thyroid hormones (TSH), PSA, Total testosterone, C-Reactive protein), the data printouts will point out at the abnormal values, with a list of those that may be significantly abnormal. Time-progress tables of the amount and percentage of subjects with low, normal or high values or with either normal or abnormal exams will be displayed.

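### Metabolic syndrome is scored on measured values only, so metabolic drugs started or intensified during follow-up can bias the +5-point test towards success

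*Protocol*

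**What the plan says.** Protocol section 8.1 (Primary Objective Measurement Variables) defines MS by waist, triglycerides, HDL-cholesterol, blood pressure and fasting glucose: "Three or more parameters must be above the upper limits for the following variables". Section 9.4.4 (Evaluation of Efficacy) uses the same five cut-offs for the primary variable: "the presence of three or more risk factors, as shown by the table below". Neither section says how to score a component under drug treatment.

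Section 6 sets the context: "This study will be conducted according to the usual clinical practice". Section 7, under Concomitant Treatments, asks for all concomitant drugs, "particularly those treating significant aspects of the metabolic syndrome, such as hypolipemiating, anti-hypertensive, hypoglycaemiating, etc. agents, should be reported". They are recorded at baseline, Month 6 and Month 12 (sections 8.4.1, 8.4.2 and 11.1). Their only stated use is in section 9.4.5, where they are coded and "summarised including the number and percentage of subjects receiving concomitant medication". Section 9.2.2 allows exclusion for banned medication, but the protocol lists none.

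For a control group, section 7 says "Not applicable". Sections 9.3.1 and 9.4.4 fix the decision rule: a two-sided 90% paired Newcombe interval for the change in prevalence, Month 12 minus baseline, with success if its upper limit is below +5%.

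**The concern.** The study is a one-arm, before-after comparison that aims to show a small increase. Anything that lowers measured Month 12 prevalence without undoing the metabolic change favours that conclusion. Suppose a patient develops raised blood pressure, triglycerides or glucose on LHRH therapy, is treated for it, and is back below the cut-off at Month 12. He can be scored MS-negative although the worsening took place. With no control group, nothing offsets this. A stronger metabolic effect would plausibly prompt more treatment, so the masking may grow with the effect being studied.

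At stake is what a success would mean. Under the rule as written, it cannot separate little metabolic worsening from worsening that was treated.

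**Working it through.** **Inputs from the protocol (section 8.3).** n = 500 evaluable; one-sided alpha 5%; margin 0.05; expected increase D = 0.020; discordant proportion h = 0.070; MS at both visits p11 = 0.290; "metabolic syndrome (MS) prevalence = 30% at study initiation". The interval is Newcombe's paired score method.

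**Input not in the documents.** k is the share of all patients whose MS at Month 12 is hidden by a drug started or intensified after baseline. It is an assumption, shown from 0 to 2%.

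**Formula.** Upper limit = D + √(dU² − 2φ·dU·dL + dL²). Here dU is the Wilson upper limit minus the estimate at Month 12, dL is the estimate minus the Wilson lower limit at baseline, and φ is the paired correlation (continuity-corrected). z = 1.645. Success means an upper limit below 0.05.

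**Step 1: reproduce the plan.** D = 0.020 and h = 0.070 give gain (0.070 + 0.020)/2 = 0.045 and loss 0.025. Simulated power at n = 500 is 0.80, as stated. A Wald check agrees: SE = √((0.070 − 0.020²)/500) = 0.0118, and Φ(0.030/0.0118 − 1.645) ≈ 0.815.

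**Step 2: put the truth at the margin.** A true increase of 0.05 with h = 0.070 gives gain 0.060 and loss 0.010. With p11 = 0.290, baseline is 0.30 and Month 12 is 0.35. Per 500 patients that is 30 new cases and 175 with MS at Month 12.

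**Step 3: apply masking.** The observed increase is 0.05 − k, whoever is masked. If new cases are masked, gain becomes 0.060 − k. If persistent cases are masked, p11 becomes 0.290 − k and loss becomes 0.010 + k.

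| k (patients per 500) | Observed increase | False success, persistent cases masked | False success, new cases masked |
|---|---|---|---|
| 0 | 5.0 points | 0.06 | 0.06 |
| 0.5% (2.5) | 4.5 | 0.12 | 0.13 |
| 1% (5) | 4.0 | 0.21 | 0.25 |
| 2% (10) | 3.0 | 0.44 | 0.62 |

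Hand check at k = 1%:
- New cases masked: h = 0.060, SE = √((0.060 − 0.040²)/500) = 0.0108, Φ(0.010/0.0108 − 1.645) ≈ 0.24.
- Persistent cases masked: h = 0.080, SE = 0.0125, giving about 0.20.

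**Step 4: vary the discordance.** If loss stays at the planned 0.025, gain is 0.075 and h is 0.10. With masking spread in proportion over all Month 12 cases, the false-success probability is 0.055, 0.104, 0.175 and 0.38 for k = 0, 0.5%, 1% and 2%. The size changes but the direction does not.

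**Scale of k.** One per cent is 5 patients: one in six of the 30 new cases, or 5/175 = 2.9% of everyone with MS at Month 12. Two per cent is 10 patients: a third of the new cases, or 5.7% of all Month 12 cases. Only 3 points separate the planned increase (2) from the margin (5).

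**The case against.** The strongest reply is that the plan is internally consistent. The objective, section 8.1 and section 9.4.4 all name the NCEP ATP III definition, and the two threshold lists agree. Measured-value MS under usual care is a legitimate quantity to estimate. The SAP is not at hand, and a treated-as-present sensitivity analysis could sit there. The masking rate is assumed. Making a treatment-adjusted definition primary, or requiring both versions to pass, would change a named endpoint and cost power against the 80% planned for one test at 500.

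Much of this stands, and it limits the point. Four stronger inferences are not supported:

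- **That the protocol misquotes its definition.** Nothing in the document shows this, and the cited source is not at hand.
- **That every patient treated at baseline is scored free of the component.** He is missed only if the drug brings the value past the cut-off; a treated patient still at or above 130/85 counts. Stable treatment at both visits lowers both prevalences and does not by itself favour success.
- **That every new drug start hides a case.** The patient must also fall below three components. Someone with four or five may stay positive, and waist is not targeted by the drugs section 7 names.
- **That a particular false-success rate applies to this study.** No figure in the documents supports one.

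The reply does not remove the problem. The protocol itself fixes the endpoint and the decision rule, and it singles out these drugs for reporting. Followed exactly, the rule lets drug starts push the primary test towards success.

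**Conclusion.** The concern holds for drugs started or intensified after baseline. In that group the measured-only rule lowers the observed increase point for point with the share of all patients masked, in the anti-conservative direction. At a true increase of 5 points with h = 0.07, false success rises from about 6% to 21–25% if 1% of patients are masked and 44–62% if 2% are. The spread reflects whether persistent or new cases are hidden. At h = 0.10 with proportional masking the figures are about 18% and 38%.

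These rates rest on an assumed k, and on taking the change with treated worsening still counted as the true one. For measured-value MS under concomitant treatment, the primary analysis answers its own question. It does not by itself support a claim of no clinically significant metabolic worsening.

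**What to change.** Keep the measured-value definition as primary and amend section 9.4.4 as follows.

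1. Add a pre-specified key sensitivity analysis with the same paired Newcombe 90% interval. In it, a component also counts as present at Month 12 if a drug for that component was started or intensified after baseline. Count lipid-lowering drugs only when the recorded indication is triglycerides or HDL, so that drugs given for LDL or prevention do not create MS.
2. Report prevalence at both visits with any treated component counted as present. This shows the effect of stable treatment on the level.
3. Tabulate new drug starts by component beside the primary result.
4. State the consequence in advance: if the sensitivity upper limit is 5% or more, the conclusion is limited to measured-value MS under concomitant treatment, with no claim that clinically significant metabolic worsening is absent.

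Cost: wording, a mapping from coded drugs to components, and possibly a less favourable conclusion. No new visits or measurements are needed, and patient care does not change. The case report form is not reproduced in the protocol, so confirm that it captures start date, dose change and indication. The primary test and its planned power stay as they are.
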